# **Table 2.**Optimized Boundaries for Halting Enrollment (i.e., "Pause")Pending Further Evaluation by the DSMB.

#### 3. SAE Reporting Plan

SAEs will be collected from time of enrollment to the end of the 30 day study window. Diseases or conditions that were present prior to the time of randomization should not be counted as adverse events unless they increase in grade or severity during the timeframe described above.

*Adverse event:* Any untoward medical occurrence associated with the use of a drug in humans, whether or not considered drug related.

*Serious adverse event:* An adverse event is considered "serious" if, in the view of either the investigator or sponsor, it results in any of the following outcomes:

- Death
- A life-threatening adverse event
- Inpatient hospitalization or prolongation of existing hospitalization
- A persistent or significant incapacity or substantial disruption of the ability to conduct normal life functions
- A congenital anomaly/birth defect
- Important medical events that may not result in death, be life-threatening, or require hospitalization may be considered serious when, based upon appropriate medical judgment, they may jeopardize the patient or participant and may require medical or surgical intervention to prevent one of the outcomes listed in this definition. Examples of such medical events include allergic bronchospasm requiring intensive treatment in an emergency room or at home, blood dyscrasias or convulsions that do not result in inpatient hospitalization, or the development of drug dependency or drug abuse.

All SAEs will be reported within 24 hours of knowledge of the event. Please refer to the Manual of Operations for SAE reporting forms and guidelines.

#### Bleeding Events:

- Major bleeds and clinically-relevant non-major (CRNM) bleeds will be considered SAEs of particular interest (if they occur during the AE reporting window).
- Based upon ISTH standardized definitions for pediatric trials [10], "Major bleeding" will be characterized by bleeding satisfying any one of the following criteria: 1) fatal;
  2) clinically overt and associated with a decrease in hemoglobin of at least 2 g/dL in a 24 hour period; 3) clinically overt and for which blood product is administered;
  4) retroperitoneal, pulmonary, or involving the central nervous system; 5) requiring surgical intervention in an operating suite.
- "CRNM bleeding" definition includes any bleeding that does not fulfill the above criteria but fulfills one of the following: 1) Bleeding requiring medical or surgical intervention to restore hemostasis, but not in an operating suite; 2) Bleeding for which medical attention is sought.

VTE events will be considered outcome events rather than SAEs, unless they otherwise fulfill the regulatory definition of an SAE (i.e., they will not fulfill the SAE criterion of investigator-defined "important medical events").

#### Adjudication of clinically-relevant bleeding, VTE, and death:

The primary outcome on safety in regard to clinically-relevant bleeding, the tertiary outcome on clinical efficacy in regard to VTE events, and all death events will be centrally adjudicated via an independent, non-blinded Clinical Endpoint Adjudication Committee (CEAC) for this non-blinded, non-randomized phase 2 trial. Refer to the Manual of Operations for reporting forms and submission instructions.

#### 4. Deviation Reporting Guidelines

A protocol deviation is defined as a variation from the protocol-directed conduct of a clinical trial. Any non- compliance with the study protocol, GCP, ICH guidelines, or a protocol-specific requirement is considered a protocol deviation. Protocol deviations will be entered into REDCap and reported to the site IRB per site policy. Deviations are reviewed in aggregate fashion at standing meetings of the COVAC-TP DSMB, via the DSMB report template. Any concerning trends can be further assessed via review of site-specific deviation logs by the COVAC-TP DSMB, as warranted, and upon request.

#### Major Protocol Deviations

Major Protocol Deviations are defined as deviations that impact patient safety or the final outcome measures of the trial. Deviations that meet the defined criteria as Major Protocol Deviations will be reported within 5 days of identification of deviation to the CCC Project Manager and the site institutional review board (IRB) per local IRB policy.

Major Protocol Deviations include, but are not limited to:

- 1. Inappropriate enrollment; expired protocol\*, violation of eligibility criteria or incomplete consent documentation
- 2. Violation of any site specific IRB requirements (e.g. If sites IRB requires both parents to sign consent)
- 3. Failure to report SAE in the 24 hour time period following knowledge of SAE\*
- 4. Failure to provide source documentation of a primary efficacy or safety outcome, as well as death event, for central adjudication by the Clinical Endpoint Adjudication Committee (CEAC).

\*items are identified as major protocol deviations, but do not disqualify participant's data to be included in the per protocol analysis.

#### Minor Protocol Deviations

Minor Protocol Deviations are defined as deviations that do not impact patient safety or the final outcome measure of the trial, but do not follow study specified guidelines. All deviations that are not determined to be major deviations are to be recorded as minor deviations. Minor Protocol Deviations include, but are not limited to:

- 1. Missed visits or visits outside study windows (except Visits 4-6 if not hospitalized at time visit is scheduled)
- 2. Missed laboratory samples or radiographic imaging that are not related to patient eligibility or study outcome (includes research specimens)

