The Schedule of Assessments is shown in Table 1. SAE monitoring and safety laboratory monitoring occurs on days 1-3, and on days 7 and 14 if the patient is still hospitalized. For all participants, pertinent clinical data will be captured as follows: results of coagulation and thrombophilia testing; nature of any major or clinically-relevant non-major bleeding episodes (as defined in Section IV B, above) during the anticoagulant therapy period (with detail as to amount of any related blood transfusion and/or any other intervention required—see also Data and Safety Monitoring Plan section); and nature of any new onset VTE (with detail as to signs/symptoms and anatomic site). PDFs of the REDCap electronic case report forms (eCRFs), as well as SAE report forms, are provided in the Manual of Operations. All SAEs and enoxaparin regimen adherence will be tracked

throughout hospitalization, and SAEs will continue to be tracked through 30 days postenrollment.

Children will complete their participation in the trial at the 30 days (+/- 2 days) postenrollment end-of-study telephone visit. As noted previously, the primary safety endpoint collection also occurs at the 30 days (+/- 2 days).

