barcode, with the association between the barcode and the participant's unique study ID maintained in the Biorepository's secure, web-based, password-protected Lab Information Management System (LIMS) maintained behind the information technology firewall at Johns Hopkins All Children's Hospital. Biospecimens will be used to identify and validate putative prognostic biomarkers in pediatric venous thrombosis and COVID-19-related illness. The genetic investigations will involve candidate genes, a genomewide association study (GWAS), and whole genome sequencing approaches in deoxyribonucleic acid. The Johns Hopkins All Children's Pediatric Biorepository uses a secure database to store all data related to the samples, behind the institutional firewall. Following completion of the protocol-specified aims, external requests for specimens in the COVAC-TP trial biobank will be vetted and made available through the National Institutes of Health (NIH), in accordance with NIH policies on data and biospecimen sharing. The second procedure will be obtaining a contrast enhanced computed tomography scan of the chest within 24 hours preceding discharge from the hospital (if not already obtained clinically during hospitalization) to assess for pulmonary emboli. Throughout their study participation, up to and including visit 6, patients will be assessed for bleeding and VTE events by their inpatient medical provider team with any SAEs being documented in the case report forms (supported by source documentation in the patient's electronic medical record) and reported to the Medical Safety Officer (MSO) as described in Section J.2. The MSO will perform an independent determination of each SAE that has been locally determined by the responsible site PI, regarding relatedness to study intervention. If EITHER determination is that the SAE is "related", the SAE will be reported to the DSMB chair. The DSMB will then assess whether any action is needed, depending on the nature of the SAE. Adverse events (and symptoms of concern for possible VTE or clinically-relevant bleeding) will be further assessed at a long-term follow up visit 30 days (+/- days) after enrollment via telephone call from a study team member.

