#### Off-Study Criteria:

- 1. In the investigator's opinion, it is in the participant's best interest to discontinue participation.
- 2. Study discontinuation by sponsor, IRB, or other regulatory body.
- 3. Lost to follow-up: Participants will not be deemed lost to follow-up until they have had no successful contact by the end of the 30-day visit window. Sites must document all attempts to contact the participant.

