4.1.4. Handling of missing data

The analysis for all the Aims will be a complete case analysis. Missing data will not be imputed.

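### No rule keeps a dosed child in bleeding follow-up to Day 30 once an investigator ends participation, and the SAP then drops children without a determined outcome

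*Protocol*

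**What the plan says.** **Leaving the study.** Item 1 of the protocol's Off-Study Criteria is "In the investigator's opinion, it is in the participant's best interest to discontinue participation". Item 2 covers a stop by the sponsor, IRB or regulator. Item 3 withholds lost-to-follow-up status until the 30-day window has closed without contact. No section says what is still collected on a dosed child who leaves under item 1.

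**Endpoint.** Protocol IV.A and SAP 3.1 define the primary outcome as clinically relevant bleeding over 30 days. Protocol IV.D adds that "the primary safety endpoint collection also occurs at the 30 days" visit. Protocol IV.H and SAP 4.2, by contrast, describe the analysed events as those of the hospital stay.

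**Analysis set.** Protocol IV.H analyses every child who received at least one dose. SAP 4.1.1 adds two conditions: no eligibility violation, and a primary outcome that was determined. SAP 4.1.4 states "The analysis for all the Aims will be a complete case analysis", with no imputation. Protocol IV.E.1 replaces only children who received no dose.

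**Deviations.** Protocol IV.J.4 says "Major Protocol Deviations are defined as deviations that impact patient safety or the final outcome measures of the trial" and "Minor Protocol Deviations are defined as deviations that do not impact patient safety or the final outcome measure of the trial". Its list of minor examples begins with "Missed visits or visits outside study windows (except Visits 4-6 if not hospitalized at time visit is scheduled".

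**The concern.** The trial exists to estimate a bleeding risk in 38 children. A child whose participation is ended early may bleed afterwards, and the documents do not say that anyone would be looking. The SAP then removes a child whose outcome was not determined, and the protocol does not replace a child who was dosed. If the reasons for ending participation are related to bleeding risk, the loss is informative. An analyst cannot recover at database lock what was never collected.

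The deviation list compounds this slightly. The visit at which the primary endpoint is collected appears to fall among examples defined as having no effect on the outcome.

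**Working it through.** **1. The plan's own figures.** Inputs: 38 evaluable children, 85% retention and up to 45 enrolled (Protocol IV.E.1); exact two-sided 90% Clopper-Pearson limits (Protocol IV.H, SAP 4.2).

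- Enrolment: 38 / 0.85 = 44.7, so 45. This agrees.
- Upper limit for x events in n: the 0.95 quantile of Beta(x + 1, n − x). For 0/38 this is 1 − 0.05^(1/38) = 7.58%; for 1/38, 11.89%; for 2/38, 15.66%. The plan prints 7.6%, 11.8% and 15.7%, so the upper limits are reproduced (11.8% is 11.89% cut off rather than rounded).
- The printed lower limits of 0 for 1/38 and 2/38 should be 0.13% and 0.94%. That does not affect this point.

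**2. What a missing dosed child does.** The number of dosed children without an outcome, m, is not in the documents. I take m = 1 to 3 as an assumption. Complete case is x/(38 − m). The worst case counts every missing child as a bleed, (x + m)/38. Upper 90% limits are in brackets.

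| Observed bleeds x | m | Complete case | Worst case |
|---|---|---|---|
| 0 | 1 | 0/37 = 0% (7.8%) | 1/38 = 2.6% (11.9%) |
| 0 | 2 | 0/36 = 0% (8.0%) | 2/38 = 5.3% (15.7%) |
| 0 | 3 | 0/35 = 0% (8.2%) | 3/38 = 7.9% (19.2%) |
| 1 | 1 | 1/37 = 2.7% (12.2%) | 2/38 = 5.3% (15.7%) |
| 1 | 2 | 1/36 = 2.8% (12.5%) | 3/38 = 7.9% (19.2%) |
| 1 | 3 | 1/35 = 2.9% (12.9%) | 4/38 = 10.5% (22.5%) |

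Hypothesis 1 asks for at most 2.6% with an upper limit of at most 11.8%, which is the 1/38 result as printed. With no observed bleeds, two missing children are enough for the worst case to miss it. With one observed bleed, a single missing child puts even the complete-case result (2.7%, 12.2%) over it.

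**3. Direction.** Take x = 1 and m = 1, so the report is 1/37 = 2.70%. If the missing child did not bleed, the full result is 1/38 = 2.63%, and the report is 0.07 points too high. If the child bled, it is 2/38 = 5.26%, and the report is 2.56 points too low. Complete case understates the incidence only if missing children bled more often than observed ones.

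**4. Where Day 30 sits in the deviation lists.** Table 1 schedules Days 0, 1, 2, 3, 7, 14 and 30. Protocol IV.F says that "up to and including visit 6, patients will be assessed for bleeding and VTE events by their inpatient medical provider team". Days 3, 7 and 14 apply only to children still in hospital, which matches the exception for Visits 4-6. Day 30 would then be Visit 7 and is not excepted. The numbering is inferred, but it fits. The second minor example sets aside samples and imaging tied to the study outcome; the first has no such carve-out for visits.

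**The case against.** Several stronger readings are tempting, and the documents do not support them.

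- **Stopping enoxaparin takes a child off study.** It does not. The regimen is for inpatient use only and participation runs to the Day 30 call (Protocol IV.D). Protocol IV.K.3 expressly deals with bleeding in children at home and off drug. Following children after the drug ends is the normal course. The gap concerns children whose participation is ended.
- **A bleed that prompts withdrawal is lost.** It should not be. Clinically relevant bleeds are SAEs, reportable within 24 hours and collected to Day 30 (Protocol IV.J.3). That rule makes no exception for off-study children, so a site could read it as continuing. It does not say so, and later bleeds remain exposed.
- **Up to 7 of 45 dosed children will be lost (45 × 0.15 = 6.75).** The retention figure directly follows the rule on replacing undosed children, so it most naturally describes them. It gives no count of dosed children without an outcome, and hence no expected number of missed bleeds.
- **The lost children are those at highest risk, so the incidence is biased downward.** This is plausible, but the documents give no reasons for withdrawal and no rates after it. Step 3 shows that the error can go either way.
- **The minor label loses data.** It does not. All deviations go into REDCap and to the DSMB in aggregate. A visit counts as missed only once its window has closed, so a 5-day report would come too late to rescue it. The major definition should also prevail over an example, since the lists are not exhaustive.

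The strongest remaining argument is the window. If only bleeding in hospital is analysed, a missed Day 30 call after discharge loses little, and Protocol IV.K.3 expects no added risk beyond 12 hours after the last regimen dose. That limits the effect of a missed call. It does not answer an exit from the study while the child is still in hospital, and the defined outcome remains 30 days.

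**Conclusion.** The point holds as a gap in follow-up joined to a restrictive analysis set. An investigator may end a dosed child's participation, no rule keeps bleeding follow-up going to Day 30, and the SAP excludes a child without a determined outcome while the protocol would analyse all who were dosed.

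The size is conditional. With one observed bleed, one missing dosed child separates 2.7% (upper limit 12.2%) from 5.3% (15.7%). This assumes 38 dosed children and that a child leaving early counts as lacking an outcome, a term SAP 4.1.1 does not define. How many children would be affected, and which way the estimate would move, cannot be derived from the documents.

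The conflict between the deviation definition and its examples is real but secondary, because relabelling recovers no data.

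**What to change.** 1. **Off-Study Criteria.** State that any child who received enoxaparin stays in bleeding, VTE and SAE follow-up to Day 30 after investigator-led discontinuation, unless consent for follow-up is withdrawn; in that case, record bleeding status at last contact. This concerns data collection only and leaves treatment decisions with the investigator.
2. **SAP 4.1.1.** Use the all-dosed safety population of Protocol IV.H. Count every adjudicated bleed observed up to last contact. Report how many dosed children lack a Day 30 outcome, and add a worst-case analysis counting each such child with no recorded bleed as a bleed. Say openly that the main estimate treats them as having no observed bleed. State which window, 30 days or hospital stay, the primary analysis uses.
3. **Protocol IV.J.4, for consistency.** Take a missed Day 30 primary-endpoint assessment out of the minor examples and list it as major, with the asterisk. Without the asterisk, the child's data could be disqualified from the per-protocol analysis mentioned there, which would worsen the loss.

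The cost is a few extra Day 30 calls and deviation reports, some wording, and one added line of results. SAP 2.5 says that 38 participants were enrolled, so items 1 and 3 may come too late for them. Item 2 needs no new data beyond last-contact status and can still be done before the SAP is finalised.

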## 5. Unanticipated Problem Reporting Guidelines

Unanticipated problems encountered or uncovered by a participating site PI must be promptly reported to the Overall PI and the CCC Project Manager via email. Unanticipated problems must also be reported to the IRB or as per IRB policy.

# 2. Alternative Treatments Considered

An alternative to this research is to not participate and have the prophylaxis approaches against HA-VTE determined by the primary medical team, with consultation of a pediatric hematologist as deemed clinically appropriate.

# 3. Adequacy of Protection Against Risks

With regard to risks of anticoagulation, participants in whom clinically-relevant bleeding develops in-patient (on enoxaparin prophylactic regimen) will receive appropriate medical attention, and those in whom bleeding develops as an outpatient (off enoxaparin prophylaxis) will be instructed to seek medical attention, as part of routine hospital discharge instructions, with re-enforcement by study personnel. However, it should be noted that this study involves standard prophylactic dosing of low-dose enoxaparin, and is therefore not anticipated to engender substantively greater bleeding risk than standard care, and is not expected to be associated with increased bleeding risk beyond 12 hours post-cessation of the in-patient low-dose enoxaparin regimen. With regard to participant confidentiality, participant identifiers will be highly limited (i.e., Health Insurance Portability and Accountability Act [HIPAA] "limited data set") in the database, and a unique study code will be used in lieu of patient names. These data will be kept for as long as necessary to conduct this and any future research and to comply with legal obligations related to research. A copy of all consent forms, which will contain participant names, will be retained in a secure and locked file in the office of the local site principal investigator. A key will be securely stored separately at the local institution from all study documents that will link the participant name to the study code. The study will be conducted under the Declaration of Helsinki and International Conference on Harmonization guidelines.

Non-English speaking families will be provided with an informed consent written in a language understandable to them and a translator provided. To the extent permissible by local IRB policy, a short form (in the patient's native language) may be used in lieu of a fully translated informed consent form.

# 4. Special Consent/Assent Plan

As this study specifically addresses the pediatric population, assent must be obtained as per IRB policy. A subset of children will be unable to provide assent as a result of age, maturity, or severity of illness. These children qualify for a waiver of assent. The remainder of children will have assent without a signature obtained at the time of parental permission to both limit research staff exposure to COVID-19 to research staff.

# 5. Potential Benefits

No definite direct benefit to the participant is expected from this study. There is a possible direct benefit in the form of a decreased risk for development of VTE; however, no such benefit may be shown by the study.

# 6. Incentives or Rewards Offered for Participation

There will be no compensation for participation in this study.

# L. Summary of Knowledge to be Gained:

The knowledge gained from this study will advance our understanding of safety, dosefinding and (on an exploratory basis) efficacy of twice-daily low-dose enoxaparin thromboprophylaxis in children hospitalized with COVID-19, and more generally, hospitalized children who are at increased risk of VTE. The tertiary aim, investigating the effect of thromboprophylaxis on respiratory-related outcomes and D-dimer, will contribute to the currently limited understanding of the pathophysiology of COVID-19 disease in children.

Appendix 2. Clinical Coordinating Center description of responsibilities.

Johns Hopkins All Children's Hospital will serve as the Clinical Coordinating Center for the study entitled "COVID-19 Anticoagulation in Children - Thromboprophylaxis (COVAC-TP) Trial". The Clinical Coordinating Center for Pediatric Multicenter Studies at JHACH provides Principal Investigators (PIs) with the infrastructure to successfully lead and conduct multicenter pediatric studies. This is accomplished by leveraging the existing resources within the JHAC Clinical and Translational Research Organization (CTRO) and All Children's Research Institute (ACRI) and applying them to the overall management and organization of a multicenter study. Led by a team of Project Managers (PMs), the CCC manages the project through each phase of the study lifecycle from start-up through close out and manuscript publication.

- In collaboration with the PI, PMs develop and revise all study documents including the protocol, consent, and operations manuals and communicates any changes to the participating sites.
- PMs assist the Principal Investigator (PI) in selecting highly-reliable sites with a proven track-record of accrual and compliance.
- PMs maintain contact information for each site.
- PMs maintain CCC IRB approvals and approved consents (local, single, or central) as well as on an ongoing basis the study's overall Trial Master File (TMF) of regulatory documents.
- PMs confirm that each participating center has an FWA on file with OHRP.
- PMs provide training to site staff at initiation as well as ongoing through monthly conference calls and webinars as well as annual investigator meetings.
- In collaboration with the PI and study biostatistician, the PM develops and tests Case Report Forms (CRFs).
- In collaboration with the JHAC CTRO Regulatory Affairs/Quality Assurance Unit, PMs perform remote monitoring of participating site's regulatory documentation and study data to ensure data accuracy, completeness and integrity.
- PMs facilitate the reporting of problem events from participating sites.
- Coordinates with the JHAC Pediatric Biorepository to design, prepare and ship kits for sample collection, receipt, and to coordinate return shipment, receipt and storage of biological samples, with accompanying sample tracking information.
